The Chief Investigator has overall responsibility for the study and shall oversee all study management. The data custodian will be the Chief Investigator. The Chief Investigator will also oversee the training of study investigators to ensure that they have the necessary competences to perform the procedures required for this study.

DURATION OF THE TRIAL / STUDY AND PARTICIPANT INVOLVEMENT

Study Duration:

The study is expected to be run for 21 months, and recruitment will begin once ethical approval has been obtained. The current expectation is to begin recruitment by November 2024 and the final study visit to occur by the end of August 2026.

Participant Duration:

The participants will be involved in the study for 16 weeks. There is no run-in period required for the study, and participants on regular medications will be advised to continue them as usual. There will be no specific follow-up after the final visit.

End of the Trial

The end of the study will be the last study visit of the last participant.

SELECTION AND WITHDRAWAL OF PARTICIPANTS

Recruitment

The study will be conducted in the Centre Of Metabolism, Ageing & Physiology (COMAP) department in the University of Nottingham's Royal Derby Hospital campus. This is a research facility based in a university building that is based on the same site and linked to a secondary care hospital. Moreover, this research department inhabits several hospital clinicians working within it and facilitates numerous studies pertaining to musculoskeletal physiology. In the last 5 years, three studies involving HIIT have been successfully recruited to and completed.

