After the fifth interval exercise, the session will end with another 2 minutes of light on-the-spot jogging. The entire HIIT protocol will last 15 minutes in total. Participants will be provided with a pulse oximeter to take home with them for monitoring of their heart rate and instructed to aim to achieve >85% of their maximum heart rate (HR_{max} – determined from the CPET on the first study day) during each session to ensure they are achieving the desired intensity. They will also receive an exercise documentation pack, in which they will be instructed to document the date and time of every exercise session, the maximum heart rate achieved during the session and any potential problems encountered.

To maintain the safety of participants during the intervention period, a number of measures will be put in place. It will be stressed to participants that if they were to develop any concerning symptoms during the HIIT sessions, they must seek immediate medical attention, either from emergency services, or their General Practitioner. We will ask participants to maintain particular awareness of the following symptoms:

- Chest pain or tightness,
- Palpitations,

- Faintness,
- Sudden pallor,
- Loss of co-ordination,
- Confusion,
- Dizziness, or
- Excessive breathlessness

These symptoms will be detailed in the exercise documentation pack so participants can refer to them during the exercise session. It will also be suggested to participants that they have another person in the near vicinity when performing the sessions (particularly the initial sessions), to ensure someone is immediately present to help obtain medical attention if required.

In addition, participants will be contacted regularly by phone, text or email throughout the intervention period by a member of the research team to discuss any problems, ensure their safety, assess compliance with the programme and obtain consent to continue. Participants in the intervention group will be contacted at least weekly for the first 4 weeks, then at least every two weeks thereafter. The control group will be contacted every two weeks. Participants will also be given a study-dedicated mobile phone number, on which they can contact a member of the research team if they have any queries or concerns that are directly related to their participation in the study.

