The control group will not be participating in any exercise intervention. Participants in this group will be instructed to make no significant changes to their current levels of physical activity for the 16-week period.

All participants will be advised to continue their regular medications as prescribed. These regular medications will have been recorded at the screening appointment and documented in the CRF.

Final Visit

At the end of the 16 weeks (approximately 72 hours after their final HIIT session), all participants will undergo their final study visit. This will follow the exact same format of the first study visit, except at the end of this study visit participants will be asked to complete a feedback questionnaire, thanked for their involvement and exited from the study. Subsequently, their General Practitioner will be sent a letter detailing their results with a copy also sent directly to them. If participants have any questions regarding their results and ongoing management, they will be advised to discuss these with their General Practitioner.

Compliance

Participants in the intervention group will be asked to complete an exercise documentation pack, in which they will be required to record details of each exercise session performed. They will be contacted by phone (or email) at regular intervals (at least weekly) and compliance will be one of the issues discussed, with reference to their documentation pack.

Participants will be expected to perform the HIIT sessions 3 times per week. However, this can be increased to 4 times if a session has been missed from the previous week. Compliance will be deemed acceptable if >80% of sessions are performed. Participants will be excluded if they:

- are unable to complete 4 or more consecutive sessions
- miss more than 7 sessions in total
- fail to complete the set exercise regime in 7 or more sessions

The number of participants excluded due to poor compliance will be recorded and reported in the study report and any potential publications.

Criteria for terminating trial

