- Improvement in overall glycaemic control – reduced HbA1c, reduced fasting glucose, reduced fasting insulin
- Reduced body weight
- Improved body composition – reduced fat mass and increased lean body mass
- Increased muscle strength and muscle function during electromyography, gait and balance analysis

- Increased fascicle length and greater pennation angle in the vastus lateralis muscle (determined by ultrasonography)
- Improved cardiorespiratory fitness – determined by increased VO_{2max} during CPET

Assessment of safety

Safety of participants will be actively monitored throughout the course of the study. Participants will be contacted regularly through the 16-week study to determine occurrence of adverse events. These will be documented in the participant's case report form and in the trial master file. There will also be a database specifically designated to the documentation of adverse events and safety concerns. This database will be reviewed regularly by the Chief Investigator and Co-Investigators. If there is a high occurrence of adverse events then this will be discussed and considerations made about altering the protocol to counteract this. If the occurrence becomes unacceptably high then the study will be terminated before completion.

Procedures for missing, unused and spurious data

This is a small research study, therefore missing data would have a significant impact on the validity of the results obtained. As such, every effort will be made to ensure the amount of missing data is kept to a minimum. Study visits will be performed by researchers who have a full and complete understanding of every aspect of the study. There will be a detailed proforma with clear instructions regarding the data that are to be collected at each timepoint. In addition, any samples requiring storage prior to analysis will be duplicated and stored in separate freezers.

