All adverse events will be assessed for seriousness, expectedness and causality. A distinction is drawn between serious and severe AEs. Severity is a measure of intensity, whereas seriousness is defined using the criteria above. Hence, a severe AE need not necessarily be serious.

Causality

Not related or improbable: a clinical event including laboratory test abnormality with temporal relationship to the study intervention which makes a causal relationship incompatible or for which other treatments, chemicals or disease provide a plausible explanation. This will be counted as “unrelated” for notification purposes.

Possible: a clinical event, including laboratory test abnormality, with temporal relationship to the study intervention which makes a causal relationship a reasonable possibility, but which could also be explained by other interventions, chemicals or concurrent disease. This will be counted as “related” for notification purposes.

Probable: a clinical event, including laboratory test abnormality, with temporal relationship to the study intervention which makes a causal relationship a reasonable possibility, and is unlikely to be due to other interventions, chemicals or concurrent disease. This will be counted as “related” for notification purposes.

Definite: a clinical event, including laboratory test abnormality, with temporal relationship to the study intervention which makes a causal relationship a reasonable possibility, and which can definitely not be attributed to other causes. This will be counted as “related” for notification purposes.

With regard to the criteria above, medical and scientific judgment shall be used in deciding whether prompt reporting is appropriate in that situation.

Reporting of adverse events

Participants will be asked to inform the research team of any adverse event occurring. The participant may choose to contact the team themselves, or inform us when a member of the research team performs one of the regular scheduled contacts with the participant. All adverse events will be recorded and closely monitored until resolution or stabilisation, even if it is unlikely that the study intervention is not the cause. The Chief Investigator shall be informed immediately of any adverse events, and shall determine seriousness and causality, in conjunction with other clinically-trained research staff and any treating medical practitioners.

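### The Protocol gives two minimum contact schedules for the HIIT arm after week 4; under either one, adverse events are sought somewhat more often in that arm than in controls.

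*Protocol*

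**What the plan says.** Under Trial / Study Treatment and Regimen, the Intervention Period section sets the contact schedule for both arms. For HIIT: "Participants in the intervention group will be contacted at least weekly for the first 4 weeks, then at least every two weeks thereafter". For controls: "The control group will be contacted every two weeks". It gives the purpose of the contacts as "to discuss any problems, ensure their safety, assess compliance with the programme and obtain consent to continue".

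The Compliance section describes HIIT contact again. It opens with "Participants in the intervention group will be asked to complete an exercise documentation pack", so the participants it goes on to describe are the HIIT arm. It then says: "They will be contacted by phone (or email) at regular intervals (at least weekly) and compliance will be one of the issues discussed". It gives no point at which the frequency falls.

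Two further sections tie these contacts to adverse events. Assessment of safety says "Participants will be contacted regularly through the 16-week study to determine occurrence of adverse events". Reporting of adverse events gives two routes: participants may contact the team themselves, or they may "inform us when a member of the research team performs one of the regular scheduled contacts with the participant".

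**The concern.** Staff who follow the Intervention Period section would move to two-weekly contact at week 5 and would then fall short of the Compliance section. The Protocol does not say which section governs.

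Two things depend on the answer.

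- **Compliance monitoring.** The Compliance section excludes participants on counts of missed or incomplete sessions, including a run of four consecutive sessions not completed, and these contacts are where compliance is discussed. How soon such a run comes to light depends on which schedule is used.
- **Finding adverse events.** Under both schedules the HIIT arm has more scheduled contacts than the control arm. More frequent asking can bring out more minor events even where the true rates are equal. Criteria for terminating trial, Methods (under Statistics) and Assessment of safety all let the investigators reconsider or end the study if adverse events become too frequent. No numerical threshold is set and there is no Data Monitoring Committee, so the recorded events inform a judgement. In a trial of 20, the control arm is the only internal yardstick for them.

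**Working it through.** The Protocol states no total number of contacts, so there is no figure of its own to reproduce. The check is a count of minimum scheduled contacts per participant.

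**Inputs**
- Length: 16 weeks (Duration of the Trial: "The participants will be involved in the study for 16 weeks").
- HIIT, Intervention Period section: one contact a week in weeks 1 to 4, then one every two weeks.
- HIIT, Compliance section: one contact a week throughout.
- Control, Intervention Period section: one contact every two weeks.
- Arm size: 20 participants allocated 1:1 (Synopsis), so 10 per arm.

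**Contacts per participant**

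| Period | HIIT, Intervention Period | HIIT, Compliance | Control |
|---|---|---|---|
| Weeks 1–4 | 4/1 = 4 | 4/1 = 4 | 4/2 = 2 |
| Weeks 5–16 | 12/2 = 6 | 12/1 = 12 | 12/2 = 6 |
| Total | 10 | 16 | 8 |

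**Ratio to control:** 10/8 = 1.25, or 16/8 = 2.0.

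**Arm totals:** 10 × 10 = 100 or 10 × 16 = 160 for HIIT, against 10 × 8 = 80 for controls.

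**Where the excess falls.** Under the Intervention Period schedule it is 10 − 8 = 2 contacts, both in weeks 1 to 4, and the minimum is equal (6 and 6) from week 5. Under the Compliance schedule it is 16 − 8 = 8 contacts: 2 in weeks 1 to 4 and 6 later. The two HIIT schedules agree up to week 4 and differ by 12 − 6 = 6 contacts after it.

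**Link to the exclusion rule.** At 3 sessions a week, 3 × 1 = 3 sessions fall between weekly contacts and 3 × 2 = 6 between two-weekly contacts. A run of four missed sessions can therefore begin and end between two-weekly contacts. It cannot do so between weekly ones.

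**The case against.** Much can be said for the plan, and most of it stands.

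- **Both HIIT statements are floors.** Weekly contact throughout would satisfy both. This is right, and it narrows the conflict to the minimum required after week 4. It does not remove it, because 6 and 12 cannot both be the minimum.
- **The excess may be small and deliberate.** Under the only section that sets out both arms, the guaranteed excess is two early contacts, placed among measures to keep participants safe while they start unsupervised exercise at home. That is a defensible choice and is not criticised here.
- **The consequence for safety conclusions is limited.** The Protocol declares no safety endpoints and plans no between-arm test of events. The termination criterion concerns events resulting from the intervention, and every event is assessed for seriousness, expectedness and causality. Controls are also contacted, have the study phone number and can report events themselves. These points confine the effect to descriptive counts and investigators' judgement.

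A reader might infer three stronger things that the documents do not support.

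- **That extra contact would itself improve weight, HbA1c or insulin results and be credited to HIIT.** The stated content of the contacts includes no diet or weight advice, and the documents give no basis for an effect or its size.
- **That the HIIT session records show a further imbalance because controls keep none.** The pack logs exercise sessions, which controls do not do, so the comparison is not like for like.
- **That both arms must have an identical contact schedule, or controls an event log.** The HIIT arm's early contact has a stated safety purpose, and how closely to follow each arm is for the sponsor to decide.

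**Conclusion.** The contradiction stands. The minimum HIIT contact in weeks 5 to 16 is 6 in one section and 12 in another, which makes 10 or 16 over the study. The two must be reconciled.

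The imbalance in looking for adverse events also stands, in modest form: 10 or 16 scheduled contacts against 8. It affects descriptive event counts by arm and the investigators' judgement on termination. It does not affect a formal safety comparison. Nor does unequal event-finding reach the primary endpoint, which is a laboratory insulin measure.

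The counts assume that every participant completes 16 weeks, that HIIT contacts run at the stated minimum, and that controls are contacted exactly every two weeks. HIIT contacts above the floor would widen the gap. The ratios of 1.25 and 2.0 are ratios of contacts, not of events. The documents give no event rates or detection rates, so any inflation of the HIIT event count cannot be sized.

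**What to change.** 1. Reconcile the Intervention Period and Compliance sections so that both state one HIIT contact schedule. Which schedule is the sponsor's choice.
2. Ask the same adverse-event questions in both arms at the two-weekly contacts they share. Have the questions cover the whole period since the last shared contact, so that an event already mentioned at an intervening HIIT contact is asked about in the same way.
3. Compare arms descriptively on events found at the shared contacts. Report separately events found only through the extra HIIT contacts or the session pack, and still take them into account for safety.
4. Record on the adverse event form how each event came to light, so that this split can be made.

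The cost is a wording change, a short common set of questions, one extra item on the form, and a little more coding and reporting work. No additional control contacts are needed.

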Title	Can High-Intensity Interval Training (HIIT) reduce the risk of diabetes relapse following discharge from the NHS Path to Remission Programme? – a pilot study
Short title	HIIT post LCD
Chief Investigator	[name]
Objectives	To determine the effect of a 16-week home-based HIIT intervention on markers of glucose metabolism and glycaemic control in individuals with T2D that have achieved diabetes remission in the NHS Path to Remission Programme.
Trial Configuration	Parallel group, non-blinded, randomised control study
Setting	Clinical research facility (Postgraduate Centre, University of Nottingham, Derby Campus)
Sample size estimate	This is a pilot study, therefore no power calculation has been performed
Number of participants	20 participants will be recruited and allocated 1:1 into intervention or control groups
Eligibility criteria	
 • Adults between the age of 18-70 years • Ability to provide informed consent. • Completed the NHS Path to Remission programme and achieved diabetes remission (HbA1c <48mmol/mol (6.5%), and off diabetes medications for at least three months)
Description of interventions	The intervention group will participate in a 16-week HIIT programme involving 3 sessions per week in their own homes. The HIIT sessions are comprised of five 1-minute intervals of body-weight exercises interspersed with 90-second active recovery periods. The control group will continue with their usual levels of activity.
Duration of study	
Each participant will be involved in the study for 16 weeks.
 
The study is expected to commence in November 2024 and be completed by the end of August 2026.

Randomisation and blinding	Participants will be randomised to the two groups using the “sealed envelope” online software. Research staff in direct contact with participants will not be blinded, however staff involved solely in analysis of samples and data will be blinded to the randomisation of participants.
Outcome measures	
The primary endpoint for this study will be beta-cell function assessed during an intravenous glucose tolerance test (IVGTT)
 
Secondary outcome measures include:
 
 • Insulin sensitivity • Overall glycaemic control • Body weight • Body composition • Skeletal muscle function

	
 • Skeletal muscle structure • Cardiorespiratory fitness (measured as VO_{2max} during cardiopulmonary exercise testing, CPET)

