In the University of Nottingham Centre Of Metabolism, Ageing & Physiology (COMAP) department, we have developed a novel home-based body-weight HIIT programme. This programme has been previously studied in a group of 18 middle-aged participants for 4 weeks, in comparison to a supervised laboratory HIIT programme and demonstrated similar results between the two groups (Blackwell *et al.*, 2017). This suggests that our home-based programme is as effective at improving cardiovascular fitness as a laboratory-based protocol.

As previously outlined, HIIT has demonstrated positive effects pancreatic beta cell function, and insulin resistance, and deterioration in these parameters, particularly beta cell function is associated with diabetes relapse. We therefore hypothesise that engaging in a HIIT intervention after achieving diabetes remission and being discharged from the Path to Remission programme will prevent the deterioration in beta cell function and insulin resistance. This would suggest that HIIT could improve maintenance of long-term diabetes remission. Thus, we are conducting this pilot study which will be the first of its kind to be performed. The results from this study will form an initial evidence-base regarding use of this intervention in this setting and will be used to inform the possible development of larger studies aimed at determining the real-world application of home-based HIIT programmes for maintenance of diabetes remission.

TRIAL / STUDY OBJECTIVES AND PURPOSE

PURPOSE

The purpose of this study is to determine the effect of a 16-week home-based HIIT intervention on markers of glucose metabolism and glycaemic control in individuals with T2D that have achieved diabetes remission in the NHS Path to Remission Programme. This will be compared against a control group who will not be involved in any exercise intervention (thus will receive usual care).

PRIMARY OBJECTIVE

Objective: To investigate whether a 16-week home-based HIIT intervention will improve beta-cell function in a group of individuals with T2D that have achieved diabetes remission, compared to a control group participating in no exercise intervention

Hypothesis: Participation in the HIIT intervention will elicit significant improvements in beta-cell function compared to not participating in any exercise intervention

SECONDARY OBJECTIVES

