Following this, the participant will be laid on a clinical examination bed in the reclined position in preparation for the IVGTT. Initially, an intravenous cannula will be inserted into the participants arm (by a trained clinical practitioner from within the research team) and fasting blood tests will be obtained. Another blood test for glucose and insulin will be obtained from the cannula 5-10 minutes later, and immediately after this, an intravenous bolus of 20% glucose will be administered, signifying the start of the IVGTT. The dose of 20% glucose administered will be calculated as 0.5g/kg body weight (up to a maximum of 35g i.e. 175ml of 20% glucose), as per standard IVGTT protocol (Bingley *et al.*, 1992). This calculation will be performed by the Co-Investigator [name], who is experienced in calculations of infusion doses. Blood samples for glucose and insulin will be obtained at 2, 4, 6, 8, 10, 20, 30, 40, 50 & 60 minutes after the initial glucose bolus. The IVGTT is a well-established method for measuring insulin sensitivity and pancreatic beta cell function (Cersosimo *et al.*, 2014; Hannon *et al.*, 2018) and has been widely utilised in studies investigating a range of exercise interventions (Slentz *et al.*, 2009; Gillen *et al.*, 2016; Mora-Rodriguez *et al.*, 2019). A total of 50ml of blood will be drawn from the participants during the IVGTT. During the IVGTT, an ultrasound of the right vastus lateralis will be performed to assess muscle cross sectional area, fascicle length and pennation angle. Additionally, participants will be asked to complete questionnaires gathering information regarding their current physical activity and quality of life.

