Two-way analysis of variance (ANOVA) will be used to determine statistically significant differences between the mean baseline and follow-up measurements of all outcomes in both groups. Additionally, the independent samples t-test will be used to compare mean changes in outcomes between the two groups and test for statistical significant differences between them. Non-parametric alternatives will be used if data are non-normally distributed. If, despite randomisation, the mean value of an outcome at baseline is different between the groups then linear regression analysis will be performed to account for the baseline difference. The significance level will be set at $p=0.05$.

Interim analysis of available data will be performed 8-10 months into the course of the study, in order to inform the funding organisation that progress is being made. Finally, in order to maintain the safety of participants, the occurrence of adverse events will be continuously monitored and if an unacceptably high incidence of such events is noted, this will be highlighted to the Chief Investigator and Co-Investigators. At this point, a decision will be made regarding continuation of the study, or if other safety procedures are required to reduce the AE occurrence rate.

Sample size and justification

This is a pilot study, as such, no power calculation has been performed to justify sample size. However, a previous study with similar participant numbers has successfully demonstrated significant improvements in beta-cell function following a HIIT intervention (Madsen *et al.*, 2015b).

Assessment of efficacy

The primary endpoint for this study is pancreatic beta-cell function assessed during an IVGTT. Thus, the HIIT intervention will be deemed efficacious if participants in the intervention group have a significantly higher beta-cell function than those in the control group, i.e. there is a greater improvement in insulin response to intravenous glucose after the 16-week intervention than after 16 weeks of usual care. Significant difference will be determined using two-way ANOVA (or other more appropriate statistical tests) as outlined above.

The secondary endpoints will provide evidence of the efficacy of the HIIT intervention on inducing improvements in other measures of cardiometabolic health and are listed below:

- Improvement in insulin sensitivity suggested by increased insulin sensitivity index (derived from the IVGTT) and reduced HOMA2-IR

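### Only controls are told to keep their activity steady, and no common exercise-free interval precedes the IVGTT, so background and recent exercise can differ between arms and visits

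*Protocol*

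**What the plan says.** **Activity during the 16 weeks.** Under Intervention Period in the protocol, the HIIT arm is asked to train at home three times a week, with the session content set out in detail. Nothing is said about the rest of its physical activity. Controls are "instructed to make no significant changes to their current levels of physical activity". The synopsis puts it more softly: "The control group will continue with their usual levels of activity".

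**Conditions before testing.** The First study visit section asks for fasting from midnight and sets no exercise condition. The Final Visit section repeats the first-visit format and places the visit of all participants "approximately 72 hours after their final HIIT session".

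**Comparator.** The primary objective compares HIIT with no exercise intervention. The Purpose section describes "a control group who will not be involved in any exercise intervention (thus will receive usual care", and Assessment of efficacy speaks of a greater improvement "than after 16 weeks of usual care".

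**Activity data.** At the first visit, and at the final visit through the same-format rule, "participants will be asked to complete questionnaires gathering information regarding their current physical activity and quality of life".

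**The concern.** This is an open-label exercise trial. Participants and the staff who contact them know the allocation, so behaviour outside the sessions can follow it. When one arm is told to keep its activity steady and the other is told nothing, a difference in non-HIIT activity can arise from the protocol itself. It would be counted as part of the HIIT effect.

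The second issue is the state in which participants reach the IVGTT. The primary endpoint (the insulin response in the first 10 minutes) and the insulin sensitivity index both come from that test. By separating the final visit from the last HIIT session, the protocol treats recent exercise as something to control, but it does so in one arm, at one visit, for one kind of exercise. The planned comparisons run both between arms and from baseline to follow-up, so both could carry a difference in recent exercise.

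**Working it through.** The protocol states no figure on this point, so the check sets the instructions side by side and counts the tests that they cover.

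**1. Activity instruction by arm (Intervention Period).**
- HIIT arm: three sessions a week; other activity not mentioned.
- Control arm: no significant change in physical activity.

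The exclusion of people in a formal exercise regime applies to both arms, but it is an entry criterion and does not govern the following 16 weeks.

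**2. Stated pre-test conditions by arm and visit.**

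| Arm | First visit | Final visit |
|---|---|---|
| HIIT | fast; no exercise interval | fast; about 72 hours after last HIIT session |
| Control | fast; no exercise interval | fast; no exercise interval |

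The 72-hour clause is written for all participants but is anchored to a session that controls never perform. In the HIIT arm it would not stop other exercise on the day before the test.

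**3. Count of tests.** Inputs: 20 participants allocated 1:1, two study visits each (synopsis; Final Visit).
- Planned IVGTTs: 20 × 2 = 40.
- With a stated interval: 10 HIIT final visits.
- Without: 40 − 10 = 30, made up of 20 first visits and 10 control final visits.

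This counts where a rule is stated. It does not measure bias.

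**4. Size.** The protocol gives no effect size, no standard deviation and no power calculation, so the effect on the primary endpoint cannot be derived. For scale only, assume a two-sample t-test on change with n = 10 per arm and a two-sided 0.05 level (the protocol gives 0.05 without sidedness). Suppose that uneven activity shifts the endpoint by δ standard deviations while HIIT itself has no effect. The test then has 18 degrees of freedom and non-centrality δ√(n/2) = δ√5.

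| Assumed δ | δ√5 | Probability of rejection |
|---|---|---|
| 0.1 | 0.22 | 5.5% |
| 0.2 | 0.45 | 7.1% |
| 0.3 | 0.67 | 9.7% |
| 0.5 | 1.12 | 18.5% |

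For comparison, 80% power on the same test needs a true difference of about 1.32 standard deviations. Under these assumptions small shifts barely raise false positives, and only a shift of around half a standard deviation does so substantially. No document figure says which δ is realistic, or its sign.

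**The case against.** The case on the other side has real force.

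- **The comparator.** A reader might infer that the trial does not make the comparison it claims, because an instruction to keep activity steady is not usual care. The documents do not support that. The primary and secondary objectives and hypotheses compare HIIT with no exercise or no exercise intervention, and the control instruction fits them. Usual care is a gloss in the Purpose section and a phrase in Assessment of efficacy; aligning it is editorial.
- **Suppressed activity.** A reader might also infer that controls are held below their normal activity. The wording rules out significant change and asks nobody to give up what they already do, in line with the synopsis. Nor is there an asymmetry in diet: no instruction restricts diet in either arm.
- **The 72 hours.** The interval keeps the test away from the last session of the only exercise that the trial introduces. Controls have no such session, and neither arm has one before the first visit. It therefore reduces an arm difference in acute exercise. This stands. What remains is the lack of a rule for other exercise.
- **Invisible uptake.** It would be wrong to say that control uptake could not be seen. VO2max, weight and body composition are measured in both arms at both visits, controls are contacted every two weeks, and activity questionnaires are collected. How those are tabulated is ordinary SAP content.
- **Unseen material.** The participant information sheet and the exercise pack are not shown and might carry further instructions.

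None of this supplies the missing instruction to the HIIT arm or a common pre-test exercise condition in the protocol.

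**Conclusion.** Two gaps stand. The protocol conditions background activity in the control arm only, and it states an exercise-to-test interval only in relation to the last HIIT session. As a result, neither non-HIIT activity nor recent exercise before the IVGTT is standardised across arms, and recent exercise is not standardised across visits.

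The count is 10 of 40 planned IVGTTs with a stated interval. The size and direction of any resulting bias are unknown: the table of shifts rests entirely on assumed values. The text does not show the HIIT comparison to be invalid.

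The point is still worth acting on. The arm difference is avoidable, the trial is open-label and small, and what participants were told and how they arrived for testing cannot be corrected at analysis.

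**What to change.** 1. **Intervention Period:** give both arms the same instruction, to make no significant change to physical activity other than the allocated HIIT sessions.
2. **First study visit and Final Visit:** apply the pre-visit interval already used for the HIIT final visit to exercise of any kind, for all participants at both visits.

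Two supporting changes are useful but secondary: report the activity questionnaire already collected by arm, and align the usual-care wording in the Purpose section and Assessment of efficacy with the comparator named in the objectives.

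The cost is a protocol amendment with matching participant-facing text, a small burden on participants before each visit, and a slightly less pragmatic comparison. No extra visits, tests or participants are needed. The changes reach only visits and intervention time still to come, so they are worth most if made early.
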